## C.2.d. Statistical Analysis and Data Management

Data Management and Reduction: All paper-based assessments (other than laboratory reports) will be entered into REDCap, a secure, web-based application designed exclusively to support data capture for research studies. REDCap provides an intuitive interface for data entry (with data validation), audit trails for tracking data manipulation, and automated export procedures for data downloading to statistical packages such as SPSS and SAS. Quarterly database management and data integrity audits will be conducted and reports submitted.

Statistics and Data Analysis (complete statistical/data analysis plan in Biostatistics Resource Core): Aim 1: Using a human laboratory paradigm, determine the impact of lofexidine on stress and drug cueinduced craving in women and men with OUDs: The primary study outcome of interest in Aim 1 is the differential craving, stress and anxiety response to a human laboratory paradigms containing both a stressor (TSST) and an opioid specific cue between participants randomized to lofexidine and placebo in addition to buprenorphine/methadone maintenance. Hypothesis 1: Lofexidine will attenuate drug craving and subjective stress response to a stress task in opioid-dependent individuals compared to individuals receiving placebo. Hypothesis 2: Lofexidine will attenuate drug craving and subjective stress response to a drug-related cue in opioid-dependent individuals. Hypothesis 3: The ameliorative effects of lofexidine on stress and cue-reactivity will be more pronounced in females than male subjects. To assess the hypothesis that lofexidine will attenuate drug craving and subjective stress response to the stressor and the opioid-related cue task, multilevel longitudinal GLMMs will be developed using all post-stressor and post-cue data. Initial models will control for study design aspects such as order (stressor or cue first), treatment assignment, and baseline craving and stress (task level). Covariate adjusted models will additionally include baseline characteristics determined to be correlated with study outcomes or those determined to be significant effect modifiers. To examine the differential effects of lofexidine on stress and cue-reactivity across female and male subjects, the models will have additional parameters added to include an indicator of participant gender and the interaction between gender and randomized treatment assignment. Relevant interactions will be assessed in all models. Least square means and associated standard errors will be assessed to compare craving and subjective stress response between treatment assignments at all time points.

Aim 2: To evaluate the impact of lofexidine on opioid craving and subjective experience of daily stressors in men and women with OUDs: The primary measures of interest for Aim 2 are craving and stress ratings in response to stress-related cues using *Cue Reactivity Ecological Momentary Assessment* (CREMA) as well as subjective experiences of daily life stressors Hypothesis 1: Lofexidine will decrease craving and decrease the subjective experience of daily stressors in opioid-dependent men and women. Exploratory Hypothesis 2: Lofexidine will be more efficacious in decreasing stress-related craving in opioid-dependent women as compared to men. To assess this hypothesis a multilevel generalized linear mixed effects models with repeated measures (GLMMs) will be developed using CREMA session response data from the 5-week period during study medication administration. Pre-cue stress and craving rating will be centered and used as a time varying covariate in all analysis. Additionally, CREMA cue response data during the 7 day baseline assessment period will be used as a time naïve covariate in all analyses. Least squares means and associated standard errors will be used for post-hoc comparisons of craving and stress response between women and men over time. Models developed to address hypothesis 2 will be utilized to examine the impact of gender on opioid use and stress-related craving during study treatment. All other relevant interactions will be assessed in all models.

Exploratory Aim 3: To evaluate the impact of lofexidine on illicit drug use in men and women with OUDs: Daily use data will be collected through morning reports via EMA and verified by urine drug screens (3 times weekly). Hypothesis 1: Lofexidine will increase the number of consecutive days abstinent as compared to placebo. Hypothesis 2: Lofexidine will be more efficacious in increasing consecutive days abstinent in women as compared to men. Time to relapse will be calculated as the days between the start of study medication (following titration; day 14) and the first day of lapse to opioid use or the laboratory stress induction day (day 40). Additionally, daily use data will be examined to determine the maximum number of consecutive days abstinent during follow up. Kaplan-Meier estimates and log-rank tests will be used to assess initial relationships between study treatment assignment and relapse while Cox proportional hazards models will be developed to assess the differential time to return to use across gender (using and appropriate interaction term). A significant interaction indicates that treatment may impact return to use time differently in women and men. Proportionality of hazards will be assessed using log-log plots and log-time interactions.

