## C.2.c.5. Phase 1: Baseline and Medication Trial

- **a. Initial Study Visit.** Participants will be trained to use CREMA and the one-week naturalistic baseline data collection period will begin following screening procedures. If it is determined that patient is ineligible based on labwork, they will be excluded and baseline procedures will end.
- **b.** Baseline Assessment (Study days 1-7). Throughout this study period, participants will come to the clinic for UDS collection. To facilitate opioid abstinence during the baseline period, we will use a standard contingency-management procedure. Participants will earn payments of \$10 for the first negative UDS and \$20 for the second. Two consecutive UDSs during the baseline week must be negative for illicit opioids in order for the subject to enter the medication treatment part of the trial. During the baseline assessment period, participants will be asked to use CREMA (described below). Subjects may have up to 10 days to provide the negative UDSs.

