- g. Virtual monitoring: In order to reduce face-to-face visits when necessary, remote monitoring may be done during the medication phase. At the randomization visit, patients will be given a wrist blood pressure cuff for at home monitoring, and they will be trained in testing orthostatic blood pressure. Patients will come to the clinic once a week for a UDS, to meet with staff/medical personnel and have ave orthostatic testing done, and receive medication refills. Two weekly visits will be conducted via Telehealth. Patients will be observed doing a saliva drug screen and doing orthostatic blood pressure testing. If patients are symptomatic or having difficulty with telehealth procedures, they may be asked to attend the clinic more frequently. Participants who are not comfortable with telehealth procedures may choose to attend clinic visits instead.
- C.2.c.5. Phase Two: Scripted Opioid Imagery and Laboratory Induction Session (Days 39 and 40). At the end of the five-week period of lofexidine or placebo administration, participants will return to complete a scripted opioid imagery taksk and a laboratory stress task (Trier Social Stress TSST). Tasks will Test, counterbalanced. Subjects will remain on study medications for the test days. Subjects who miss their scheduled visits may be re-scheduled for up to one week. a. Session Preparation. Participants will be instructed to arrive at 8:00am on the test days, and to avoid caffeinated beverages since caffeine can introduce variability in heart rate response. If the individual is nicotine-dependent, (s)he will be provided with a nicotine patch throughout their study visit. Upon arrival, the participant will be breathalyzed and

|            | TAB             | BLE 3: LAB TESTING TIMELINE                                |  |  |
|------------|-----------------|--|--|--|
|            | 8:15am          | UDS, Saliva  |  |  |
|            | 8:35 am         | Relaxation   |  |  |
| Test Day 1 | 8:55am          | Baseline 1 Subjective, physiologic, endocrine measurement  |  |  |
| st [       | 9:00am - 9:15am | TSST/Imagery   |  |  |
| Te         | 9:15am          | Subjective, physiologic, endocrine measurement             |  |  |
|            | 9:20am          | Subjective, physiologic, endocrine measurement             |  |  |
|            | 9:45am          | Subjective, physiologic, endocrine measurement             |  |  |

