|            | 10:15am         | Subjective, physiologic, endocrine measurement             |  |  |
|            |                 |  |  |  |
|            | 815am           | UDS, Saliva  |  |  |
|            | 8:35am          | Relaxation   |  |  |
| Day 2      | 8:55am          | Baseline 1: Subjective, physiologic, endocrine measurement |  |  |
|            | 9:00am          | Opioid imagery/TSST  |  |  |
| Test       | 9:05am          | Subjective, physiologic, endocrine measurement             |  |  |
| _          | 9:10am          | Subjective, physiologic, endocrine measurement             |  |  |
|            | 9:35am          | Subjective, physiologic, endocrine measurement             |  |  |
|            | 10:05 am        | Subjective, physiologic, endocrine measurement             |  |  |

will provide a urine sample to be tested for drugs of abuse. For women, a pregnancy test will be done prior to the urine drug screen, and saliva will be collected for estrogen and progesterone measurement.

- **b.Progesterone and Estrogen.** As there is significant individual variability in progesterone and estrogen levels across the menstrual cycle, measurement of progesterone and estrogen at the time of testing in combination with the menstrual cycle history will allow us to approximate the menstrual cycle phase as well as to utilize all participants' data with absolute progesterone and estrogen levels as continuous measures.
- **c. Design timing.** Subjects will first undergo a progressive relaxation task. Baseline assessments of subjective, hormonal (cortisol), and physiologic measures (blood pressure and heart rate) will be collected following relaxation, 5 minutes before the stressor or imagery; TSST takes 15 minutes, and the imagery takes 5 minutes. At the end of the stressor of drug cue, a salivary sample will be collected to assay cortisol and physiological (blood pressure and heart rate) and subjective measures (Mood Rating Scale, Opioid Craving Questionnaire, STAI) will be obtained. Measurements will also be obtained at 5- 30-, and 60-minutes post-task.
- d. Trier Social Stress Task (TSST) is a standardized psychological stress challenge which has been used extensively in research studies. A meta-analysis supports its utility for evoking a HPA axis stress response in a laboratory setting (Dickerson & Kemeny, 2004). It has induced a robust and reliable physiological stress

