- **f. Assessments.** Self-Report Measures. Mood Rating Scale: As described above and used with the CREMA sessions, to allow for cross-task comparisons. State-Trait Inventory (STAI): The STAI is a 20-item self-report scale (Spielberger, 1983) employing a Likert-scale format with four responses per item (1-4). Ten of the STAI items measure feelings of stress and anxiety, while the remaining ten items measure feelings of relaxation. The STAI has good psychometric properties. Opioid craving will also be measured using a Likert scale format. We have had good success with this in prior studies in OUDs (Back et al., 2014) Physiological Measures. Heart rate and blood pressure will be measured using an intermittently inflatable cuff as indices of physiological arousal during the test session. Hormonal Measures. Cortisol: Cortisol will be measured in unstimulated passive saliva using the Salimetrics expanded range, high sensitivity salivary cortisol enzyme immunoassay kit. This kit has a lower sensitivity level of <0.003 μg/dL. The correlation between salivary and serum cortisol has been shown to be high (r=0.91, p<0.0001). Cortisol is commonly measured as an indication of stress response in human laboratory studies.

Modifications may be made to lab day procedures if necessary for patient and staff safety, ie fewer confederates, remote procedures.

- **g. Discharge.** Following assessments, participants will be given instructions to taper their lofexidine over the next five days. A member of the research staff will be available to discuss management of any craving or urges to use any substance if craving remains elevated at the end of study procedures.
- **C.2.c.6. Follow-up Assessment (Days 41-47).** During a one-week follow-up period, lofexidine will be tapered... They will come to the two times during the taper for BP monitoring (0.72 BID for two days, 0.36 mg BID for 2 days, 0.36 QD for 1 day). After five days, participants will return to the clinic and return clinic-provided phones, complete a questionnaire regarding their experience with the CREMA and REDCap surveys, and be provided referrals to treatment if interested.

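### The initial Aim 1 models pre-specify no pre-randomisation measure of craving or stress, although baseline-week CREMA ratings are already collected and Aim 2 adjusts for baseline CREMA data

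*Combined protocol and SAP*

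**What the plan says.** - **Aim 1, initial models** (C.2.d): "Initial models will control for study design aspects such as order (stressor or cue first), treatment assignment, and baseline craving and stress (task level". No baseline-week measure is named.
- **Aim 1, further models** (C.2.d): "Covariate adjusted models will additionally include baseline characteristics determined to be correlated with study outcomes", or found to be effect modifiers. No criterion is given. The section also refers to a "complete statistical/data analysis plan in Biostatistics Resource Core", which is not part of these documents.
- **Timing of the task-level baseline** (C.2.c.5, Phase Two, Design timing): "Baseline assessments of subjective, hormonal (cortisol), and physiologic measures (blood pressure and heart rate) will be collected following relaxation", five minutes before the stressor or imagery. Phase Two takes place on days 39 and 40, and "Subjects will remain on study medications for the test days".
- **Pre-randomisation ratings** (C.2.c.5, Phase 1, Baseline Assessment, study days 1-7): "During the baseline assessment period, participants will be asked to use CREMA". The CREMA Assessment paragraph lists craving and stress among the rated items.
- **Shared scale** (Phase Two, Assessments), on the laboratory Mood Rating Scale: "As described above and used with the CREMA sessions, to allow for cross-task comparisons".
- **Aim 2** (C.2.d): "CREMA cue response data during the 7 day baseline assessment period will be used as a time"; the sentence goes on to make them a time-constant covariate for every Aim 2 analysis.
- **Sizing** (Power and Sample Size): the sample size is set on the treatment x sex interaction in the laboratory response, with d = 0.64.

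**The concern.** There is no laboratory session before treatment, and the one baseline in the initial Aim 1 models is measured after about a month on lofexidine or placebo. Differences in craving and stress that participants bring into the trial can leave the error term only as far as that on-treatment rating happens to carry them. The Aim 1 comparisons of treatment, and of treatment by gender, are comparisons between people, so this variation counts directly against their precision.

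The named stratification factors are other substance use and childhood trauma. They do not include craving, stress or gender, so nothing in the design protects against a chance difference in prior craving between arms within gender. Aim 2 already accepts the principle of adjusting for baseline CREMA data; Aim 1, which holds the test the trial is sized on, does not fix it in advance.

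**Working it through.** **The plan's own figure.** Inputs from Power and Sample Size: d = 0.64 (SD = 1), 80% power, 5% type 1 error (two-sided assumed), 39 per sex-by-arm cell, 136 randomised, 25% attrition.

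- Two-group comparison: n = 2(1.96 + 0.84)²/0.64² = 38.3, so 39 per group, with 80.7% power. This reproduces 39, but as the size of a two-group comparison.
- Interaction as a difference of differences: SE = √(4/n), with n per cell. At n = 39 the power is 51.5%; 80% needs 4(1.96 + 0.84)²/0.64² = 76.6, so 77 per cell.
- Completers: 136 x 0.75 = 102, or 25.5 per cell.

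The stated 80% for the interaction is therefore not reproduced. That is a separate matter; the corrected interaction formula is used below only to show what the covariate could add.

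**Adding baseline-week CREMA.** Let r be its partial correlation with the laboratory outcome, given the covariates already in the model. Residual variance is multiplied by 1 − r², so SE = √(4(1 − r²)/n) and power = Φ(0.64/SE − 1.96). The documents give no value of r; the range is an assumption.

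| r | 1 − r² | SE, 25.5 per cell | Power, 102 completers | Power, all 136 (34 per cell) |
|---|---|---|---|---|
| 0 | 1.00 | 0.396 | 36.5% | 46.3% |
| 0.1 | 0.99 | 0.394 | 36.8% | 46.6% |
| 0.3 | 0.91 | 0.378 | 39.5% | 49.8% |
| 0.4 | 0.84 | 0.363 | 42.2% | 53.0% |
| 0.5 | 0.75 | 0.343 | 46.3% | 57.7% |

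**With the task-level rating kept.** What matters is what CREMA adds to that rating. Let a be the correlation of task rating with outcome, b of CREMA with outcome, and c of CREMA with task rating. Then partial r = (b − ac)/√((1 − a²)(1 − c²)). Take a = c = 0.5 (assumed) and 102 completers, where power with the task rating alone is 46.3%:

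- b = 0.3: partial r = (0.3 − 0.25)/0.75 = 0.07; power 46.4%, a gain of 0.1 points.
- b = 0.4: partial r = 0.15/0.75 = 0.20; power 47.8%, a gain of 1.5 points.
- b = 0.5: partial r = 0.25/0.75 = 0.33; power 50.8%, a gain of 4.5 points.

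These depend on the chosen correlations. With a and c each between 0.3 and 0.7 and b at 0.3 or 0.5, the gain runs from none to about 9 points (61.9% to 70.6% at a = 0.7, b = 0.5, c = 0.3).

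**Chance imbalance.** A standardised baseline has the same 0.396 SD standard error on the interaction contrast. With no other baseline in the model and r = 0.3 to 0.5, an imbalance of that size shifts the estimate by 0.396 x 0.3 = 0.12 to 0.396 x 0.5 = 0.20 SD, or 19% to 31% of 0.64.

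**The case against.** The strongest reply is that the covariate is not shut out. The covariate-adjusted models may take in any baseline characteristic that correlates with outcome. If the rule were a 5% correlation test (an assumption), a correlation of 0.3 would be picked up with about 87% probability at 102 participants, and 0.4 with about 99%. So a reader who infers that Aim 1 excludes CREMA altogether goes too far. What stands is narrower: entry depends on the trial's own outcome data under an unstated criterion, and the initial models lack the covariate in any case. The complete plan held elsewhere may already name it; these documents cannot show that.

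Second, the task-level rating comes from the same person minutes before the task and may already absorb much of what CREMA would explain. That is a fair limit on the gain, as the illustrations show. It does not make that rating a pre-randomisation measure.

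Third, three tempting statements do not survive the text:

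- CREMA is not the only pre-randomisation measure of both constructs. The Perceived Stress Scale is among the screening instruments (C.2.c3). For craving, no other pre-randomisation rating was found.
- The shared scale covers the Mood Rating Scale items only. The laboratory also uses the STAI and a separate Likert craving measure.
- Aim 2's covariate is cue response, not a mean rating, so it supports the principle but is not the same variable.

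Finally, omitting a prognostic covariate from a randomised comparison does not bias it, and the standard error already allows for chance imbalance. That stands in full.

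**Conclusion.** The point holds as a free improvement. The initial Aim 1 models pre-specify no pre-randomisation craving or stress measure, although suitable ratings are already collected.

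The direction of the benefit is clear; its size is not. With 102 completers and d = 0.64, power would move from about 37% to between 37% and 46% for an assumed partial correlation of 0.1-0.5. With the task-level rating kept, and both its correlations (with outcome and with CREMA) set at 0.5, the gain is about 0.1 to 4.5 points. It may be negligible. A reader might infer a saving worth 10-33% more participants, since 1/(1 − r²) is 1.10 at r = 0.3 and 1.33 at r = 0.5. That takes for granted a partial correlation of 0.3-0.5, which the documents do not support.

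Nor does the covariate rescue the sample size. Reaching 80% interaction power would need 1 − r² = 39/76.6 = 0.51, so r of about 0.70, even with 39 per cell. With 25.5 per cell it would need 1 − r² = 25.5/76.6 = 0.33, so r of about 0.82.

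**What to change.** In C.2.d, Aim 1, add to the models for Hypotheses 1-3, as a fixed covariate chosen in advance, each participant's mean pre-randomisation CREMA craving rating (craving models) or stress rating (stress models). State which ratings form the mean, for example the uncued and pre-cue ratings, and how a participant with no usable baseline rating is handled. Do not leave its entry to the correlation-based rule. If the complete plan held elsewhere already does this, say so in this section.

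The cost is a short addition to the analysis text and one degree of freedom per model; no new data are needed. The change is worthwhile whatever is decided about the on-treatment task-level rating. The sample-size calculation needs its own correction.

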## Power and Sample Size (complete sample size justification available in Biostatistics Resource Core):

The current study is powered on the primary Aims 1 and 2. In the proposed study, response to a laboratory stressor, CREMA cue response and daily use data will be tested using GLMMs (assuming a Gaussian distribution) and the study will be powered to sufficiently address the least of the study treatment effect sizes determined to be clinically meaningful for the study hypothesis. Aim 1: Sinha and colleagues (Sinha, et al 2007), in a small pilot sample, demonstrated that lofexiding in combination with naltrexone attenuated craving and anger in response to laboratory drug and stress cues as compared to naltrexone alone. Results indicate a larger change in opioid craving scores in response to drug-related and stress cues occurs in placebo participants than lofexidine treated participants [Drug related cue response  $\Delta$ =2.2; SDP=2.6; between group Cohen's d=0.85, p<0.05 and stress cues response  $\Delta$ =2.1; SDP=2.4; between group Cohen's d=0.88, p<0.05]. Moreover, Fox and colleagues (2014) conducted a trial of quanfacine in cocaine-dependent individuals and noted stress and craving response to stress and drug-related imagery. They noted significant gender differences across treatment assignment for craving and stress response to drug-related imagery [Craving  $\Delta$ =3.0; SDP=3.8; Treatment x Sex Intx Cohen's d=0.79, p<0.05; Negative Emotion  $\Delta=3.0$ ; SDP=2.9; Treatment x Sex Intx Cohen's d=1.0, p<0.05]. Sample sizes in both the Sinha and Fox studies were somewhat small. Smaller but still clinically relevant effect sizes in an adequately powered study are anticipated. Therefore, a 20% reduction in craving and stress response from the previous studies is anticipated in the current design (Cohen's d=0.64 for the sex x treatment interaction on craving response). Aim 2: Kowalczyk and colleagues (2015), showed that daily life craving reports as measured by EMA were significantly reduced in opioid using participants randomized to clonidine as compared to placebo [6.3% (95% CI=5.6-7.1) vs. 11.8% (10.9-13.0); between group Cohen's *d*=1.6]. To assess the least of the differences anticipated in project 2, a sample size of 39 participants randomized to each female and males across active lofexidine and placebo groups would provide 80% power with a type 1 error rate of 5% to detect the treatment x sex interaction in craving and stress response to laboratory drug based cues (total n=156; 78 per group). We anticipate 25% attrition between randomization and the end of the 5-week active treatment period. Thus, inflating the necessary sample size to 68 participants randomized per treatment group with a total of n=136 randomized participants will provide adequate power.

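### Aim 2: the on-drug pre-cue ratings are a covariate in every analysis, which suits cue reactivity but not Hypothesis 1's claim of lower overall craving and daily-stressor experience

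*Combined protocol and SAP*

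**What the plan says.** Section C.2.d, Aim 2, names two kinds of measure. "The primary measures of interest for Aim 2 are craving and stress ratings in response to stress-related cues" is the first; the sentence then adds "as well as subjective experiences of daily life stressors". Hypothesis 1 reads: "Lofexidine will decrease craving and decrease the subjective experience of daily stressors in opioid-dependent men and women". It is the only Aim 2 hypothesis not labelled exploratory.

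The mixed models "will be developed using CREMA session response data from the 5-week period during study medication administration". Two covariates apply to every analysis:
- the on-drug rating: "Pre-cue stress and craving rating will be centered and used as a time varying covariate in all analysis";
- a pre-randomisation value: "CREMA cue response data during the 7 day baseline assessment period".

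The text does not say whether centring is by grand mean or person mean. The only least-squares-means comparison it names for Aim 2 is women against men.

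Section C.2.c.5, item c (CREMA Assessment), describes three data streams: a daily no-picture rating of stress, craving and mood; a daily survey covering stressful events; and picture sessions with stressful or neutral images. It separates ambient state from evoked response. For picture sessions it describes a post-cue rating only.

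The Power and Sample Size section says that "response to a laboratory stressor, CREMA cue response and daily use data will be tested using GLMMs". Its Aim 2 effect size comes from a clonidine trial that "showed that daily life craving reports as measured by EMA were significantly reduced in opioid using participants randomized to clonidine", which is an ambient measure.

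**The concern.** A covariate measured after randomisation, on study drug, can carry part of the treatment effect. For cue reactivity that is intended: the question is how far the rating moves given where it stood just before the picture. Hypothesis 1 asks something else, namely whether craving and the experience of daily stressors fall overall. If lofexidine lowers craving throughout the day, the pre-cue rating falls too, and adjusting for it can subtract part of the effect that Hypothesis 1 asserts.

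The rule also does not fit the data that bear most directly on Hypothesis 1. A no-picture rating or a daily survey item has no pre-cue value, and baseline cue response is not the baseline of the same measure.

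At stake are the reported size of an overall effect and, if that effect is small and mainly ambient, the power to detect it.

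**Working it through.** **The plan's own Aim 2 figure.** The Power section gives 6.3% (CI 5.6 to 7.1) against 11.8% (10.9 to 13.0) and d = 1.6. Section A.6 gives 118 participants; 59 per arm is assumed here.
- SDs: (7.1 − 5.6)/(2 × 1.96) × √59 = 2.94, and (13.0 − 10.9)/(2 × 1.96) × √59 = 4.11.
- Pooled SD: √[(2.94² + 4.11²)/2] = 3.58.
- d = (11.8 − 6.3)/3.58 = 1.54, close to 1.6.

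The figure is roughly reproduced, and it describes ambient craving. An ambient component is therefore plausible on the plan's own evidence. Section A.6 also reports that stress and craving were partly decoupled in the same trial, so a reactive component is plausible too.

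**Algebra.** Let τ be the total treatment effect on the post-cue rating. Let δ₁ and δ₂ be the treatment effects on pre-cue stress and craving, with slopes b₁ and b₂.
- Grand-mean centring: adjusted coefficient = τ − (b₁δ₁ + b₂δ₂).
- Person-mean centring: the covariate averages zero within each person, so it carries no difference between arms and the coefficient stays τ.

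With one covariate under grand-mean centring:
- wholly ambient effect (δ = τ): τ(1 − b) remains, so a share b is removed;
- half ambient, half reactive (δ = τ/2): a share b/2 is removed;
- purely reactive (δ = 0): nothing is removed.

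**Check by simulation** (random-intercept model, 1,000 people, 17 sessions each, ambient effect −1.0, one covariate):

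| Assumed b | Total effect | Grand-mean adjusted | Share removed | Person-mean adjusted |
|---|---|---|---|---|
| 0.3 | −0.97 | −0.65 | 32% | −0.97 |
| 0.5 | −1.00 | −0.46 | 54% | −1.00 |
| 0.7 | −1.00 | −0.31 | 69% | −1.00 |
| 0.9 | −0.98 | −0.11 | 89% | −0.98 |

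Shares are computed before rounding. For a purely reactive effect, grand-mean adjustment gave −1.05 against −1.04, so nothing was lost. With within- and between-person slopes of 0.5 and 0.9, the fitted slope was 0.52 and the adjusted estimate −0.42 of −0.90. The loss follows the fitted slope.

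**At the trial's size.** Completers: 136 × 0.75 = 102. About 14 stress-cue sessions each are assumed (33 days on drug, half with stressful pictures, about 87% completed). The total effect is an assumed 0.5 SD, and the fitted slopes are about 0.90/0.74/0.57/0.42/0.30. All variances are assumed.

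| Nature of effect | Share removed, grand mean | Power with covariate | Power without |
|---|---|---|---|
| All ambient (1,000 replicates) | 90/74/57/43/30% | 18/64/87/94/96% | 98% |
| Half and half (400 replicates) | 45/36/28/21/15% | 98.5–100% | 97–99% |
| All reactive (400 replicates) | about 0% | 100% | 97–99% |

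**Applied to d = 1.6, SD held fixed, b = 0.3/0.5/0.7/0.9.**
- Wholly ambient: 1.6 × (1 − b) = 1.12/0.80/0.48/0.16.
- Half and half: 1.6 × (1 − b/2) = 1.36/1.20/1.04/0.88.

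In the trial-size simulation of a wholly ambient 1.6 SD effect, power was still 88% at the steepest slope and 100% at the other four.

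**The case against.** Four points can be made for the plan.

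1. **The model may already cover ambient craving.** The CREMA section says ratings can be taken with or without pictures and calls the no-picture rating a session, so the Aim 2 model can be read to include it. This stands. A reader might infer that the plan has no model that could cover ambient craving; the text does not support that. The covariate rule still does not fit those sessions, and the daily survey has no explicit model on either reading.

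2. **Pre-cue adjustment is right for the leading measure.** Cue response is named first under Aim 2, and the data and safety monitoring summary calls stress reactivity the primary outcome. This stands too. The covariate loses nothing on a purely reactive effect and slightly raises power, so it should stay in that model. An estimate that leaves out ambient change answers a different question; it is not a wrong answer to the reactivity question.

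3. **The loss needs several conditions.** The cue-session model must serve as the test of Hypothesis 1, centring must be by grand mean, and the effect must be at least partly ambient. The documents settle none of these. A reader might infer that the trial will understate lofexidine's effect by 30% to 90%; that does not follow.

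4. **The text is a summary.** Section C.2.d places the complete analysis plan in the Biostatistics Resource Core, which is not among the documents. It may resolve the matter.

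**Conclusion.** The point holds in a limited form. As written, the rule puts an on-drug covariate into every Aim 2 analysis. It suits cue reactivity, and it suits neither the ambient ratings nor the daily-stressor reports on which Hypothesis 1 depends.

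The loss is conditional. With grand-mean centring and one covariate, about a share b of a wholly ambient effect is removed (30% to 90% for an assumed b of 0.3 to 0.9), and about half that for an evenly mixed effect. For a purely reactive effect, or with person-mean centring, the loss is zero. With both pre-cue ratings in the model it is the sum of two terms.

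A general loss of power is another inference that the documents do not support. In these simulations power fell only for a wholly ambient effect, and seriously only at steep slopes with modest effects. The slope, the variances and the 0.5 SD effect are all assumptions. The change is worth making, but this does not show that the Aim 2 result would be wrong.

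**What to change.** 1. Restrict the pre-cue covariate to the cue-reactivity model. Label that result as reactivity conditional on the on-drug pre-cue level.
2. Test Hypothesis 1 with a stated lofexidine-versus-placebo contrast in mixed models of (a) the no-picture craving and stress ratings and (b) the daily-stressor reports. Adjust each only for the baseline-week value of the same measure, with no on-drug covariate.
3. While editing, state the type of centring and when the pre-cue rating is taken.

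If the Biostatistics Resource Core plan already says this, copy its wording into section C.2.d.

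The cost is SAP wording and one extra model per outcome, on data already collected. In the simulation with 102 completers and a wholly ambient effect, the ambient model lost no power against the cue-session model without the covariate: 69–70% against 63–64% at an assumed 0.3 SD, and 99% against 98% at 0.5 SD.
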